2.1 Risk / Benefit Assessment

Regarding the tildrakizumab treatment, this is a FDA approved medication for psoriasis. The same risks/benefits assessment for a psoriatic patient in our clinics as to whether to start this medication apply.

Regarding the skin biopsy, there is minimal risk to patients as punch biopsies are standard dermatologic procedures that are performed frequently with minimal side effects, which include bleeding, pain, infection, scar, changes in skin coloration, and allergic reaction to anesthesia. Knowledge may be gained about health conditions and patient may derive a feeling of contribution to knowledge in the health field

3 STUDY OBJECTIVES

3.1 Primary Objective

Our primary objective is to identify the genes that are differentially expressed in psoriatic skin between patients that do and do not respond to tildrakizumab

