6	SUBJECT SELECTION	9
6.1	Study Population	9
6.2	Inclusion Criteria	9
6.3	Exclusion Criteria	9
7	CONCURRENT MEDICATIONS	9
7.1	Allowed	10
7.2	Prohibited	10
8	STUDY TREATMENTS	10
8.1	Method of Assigning Subjects to Treatment Groups	10
8.2	Blinding	10
8.3	Test and Control Formulation	10
8.4	Supply of Study Medication at the Site	10
8.5	Study Medication Accountability	11
8.6	Measures of Treatment Compliance	11
9	STUDY PROCEDURES AND GUIDELINES	11
9.1	Clinical Assessments	11
9.2	Pharmacokinetic Measurements	12
10	EVALUATIONS BY VISIT	12
10.1	Visit 1	12
10.2	Visit 2 (2 weeks after Visit #1)	12
11	ADVERSE EXPERIENCE REPORTING AND DOCUMENTATION	13
11.1	Adverse Events	13
11.2	Serious Adverse Experiences (SAE)	14
11.3	Medical Monitoring	15

- 12 DISCONTINUATION AND REPLACEMENT OF SUBJECTS15**
 - 12.1 Withdrawal of Subjects15
 - 12.3 Replacement of Subjects15
- 13 PROTOCOL VIOLATIONS15**
- 14 STATISTICAL METHODS AND CONSIDERATIONS16**
 - 14.1 Data Sets Analyzed16
 - 14.2 Demographic and Baseline Characteristics16
 - 14.3 Analysis of Primary Endpoint16
 - 14.4 Analysis of Secondary Endpoints16
 - 14.5 Interim Analysis16
 - 14.6 Sample Size and Randomization16
- 15 DATA COLLECTION, RETENTION AND MONITORING16**
 - 15.1 Data Collection Instruments16
 - 15.2 Data Management Procedures17
 - 15.3 Data Quality Control and Reporting17
 - 15.4 Archival of Data17
 - 15.5 Availability and Retention of Investigational Records17
 - 15.6 Monitoring18
 - 15.7 Subject Confidentiality18
- 16 ADMINISTRATIVE, ETHICAL, REGULATORY CONSIDERATIONS18**
 - 16.1 Protocol Amendments18
 - 16.2 Institutional Review Boards and Independent Ethics Committees18
 - 16.3 Informed Consent Form19
 - 16.4 Publications19
 - 16.5 Investigator Responsibilities20

LIST OF ABBREVIATIONS

none

PROTOCOL SYNOPSIS

TITLE	PREDICTING TREATMENT RESPONSE FOR INFLAMMATORY SKIN DISEASE
SPONSOR	self
FUNDING ORGANIZATION	none
NUMBER OF SITES	1
RATIONALE	To develop a predictive algorithm to determine whether a given patient with psoriasis will respond to one of the multiple specific pathway blocking FDA-approved psoriasis biologic medications.
STUDY DESIGN	interventional trial with molecular profiling of skin samples
PRIMARY OBJECTIVE	To obtain pre-treatment psoriatic skin samples for molecular profiling prior to treatment with tildrakizumab to correlate with and to predict treatment response
SECONDARY OBJECTIVES	
NUMBER OF SUBJECTS	10

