SUBJECT SELECTION CRITERIA	
Inclusion Criteria: > 18 years of age, Patients with moderate-severe psoriasis or atypical psoriasis with either non-biologic treatment failure or > 5% body surface area affected.
 
Exclusion Criteria: tuberculosis, active serious infection, active systemic malignancy, or received a systemic medication for psoriasis within 3 months of study screening.

TEST PRODUCT, DOSE, AND ROUTE OF ADMINISTRATION	Tildrakizumab 100 mg subcutaneous injection
CONTROL PRODUCT, DOSE AND ROUTE OF ADMINISTRATION	n/a

DURATION OF SUBJECT PARTICIPATION AND DURATION OF STUDY	
The time commitment for the first visit will be approximately 1.5 hours to discuss the study, consent the patient, and perform the biopsy.
 
The second visit will last approximately 15 minutes
 
The third and fourth visits will last approximately 30 minutes.
 
With a total time committment of ~ 2 hrs 45 minutes

CONCOMMITANT MEDICATIONS	
Allowed:
 
Prohibited: other systemic medications for psoriasis

EFFICACY EVALUATIONS	
PRIMARY ENDPOINT	
 molecular gene expression profiling of skin cell populations.
SECONDARY ENDPOINTS	
 Psoriasis Area and Severity Index (PASI) score
OTHER EVALUATIONS	
SAFETY EVALUATIONS	
Re-evaluation of biopsy site at follow-up visit in 14 days for wound infection
 
In person medical visit for physical exam and history 4 weeks and 16 weeks after start of medication

PLANNED INTERIM ANALYSES	
When approximately 50% of patients have completed the study through Visit 4, an interim analysis for safety will be conducted by the investigator. Serious adverse events will be monitored by the committee on an ongoing basis throughout the study.

STATISTICS Primary Analysis Plan	
We will rely heavily on RNA-seq analysis, in some cases complemented with DNA sequencing and protein assessments. The RNAseq data will be normalized and compared in diseased vs normal skin and differential expression discerned at a significance level of 5% in a single test, in a two-group comparison, using a Negative Binomial mode. Numerous qualitative analyses will be performed as well.

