1 BACKGROUND

Cutaneous inflammation represents the most common skin pathology, placing pervasive burdens on health care cost and quality of life. Biologic immunomodulatory therapies now enable improvement of major rashes such as psoriasis and atopic dermatitis; however, a significant minority of patients do not adequately respond to these medications. Given the multiple medication options that target different inflammatory pathways, significant expense and serious side effects of these immunomodulatory medications, it is imperative that we develop mechanisms to better predict whether a patient will respond to a given drug.

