5 CRITERIA FOR EVALUATION

5.1 Primary Efficacy Endpoint

We will evaluate if there are genes which are statistically significantly upregulated or downregulated in specific cell populations, based on RNA sequencing.

For assessment of psoriasis improvement, we will use the Psoriasis Area and Severity Index (PASI) scoring system.

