13.4 Analysis of Secondary Endpoints

There are no secondary endpoints.

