13.6 Sample Size and Randomization

10 samples will be collected for initial analysis. Distribution-based statistical analysis indicates that two-fold differences in gene transcription will be detected at this size.

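### Section 3.1 frames the primary question as a yes/no responder contrast in 10 treated patients, with nothing to secure enough non-responders; use PASI improvement as a continuous covariate instead

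*Combined protocol and SAP*

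**What the plan says.** - **Objective.** Section 3.1 seeks the genes whose expression in lesional skin differs between "patients that do and do not respond to tildrakizumab". This is a two-group question about pre-treatment lesional skin.
- **Design.** Section 7.1 has every patient treated, and section 13.6 says "10 samples will be collected for initial analysis". The number in each response group is therefore random.
- **Response measure.** Section 5.1: "For assessment of psoriasis improvement, we will use the Psoriasis Area and Severity Index (PASI) scoring system". No cut-off, time point or expected response rate is given.
- **Expected non-response.** Section 1 says only that "a significant minority of patients do not adequately respond to these medications", speaking of biologics in general.
- **Analysis.** The synopsis gives the primary objective as obtaining samples "to correlate with and to predict treatment response". Its analysis plan, however, specifies a Negative Binomial two-group test at 5%: "The RNAseq data will be normalized and compared in diseased vs normal skin". Section 2 speaks of comparing profiles with treatment response. Section 13.3 names neither groups nor a covariate.
- **Visits.** PASI appears in none of the visit lists (9.1 to 9.4) and not in Appendix 1.
- **Secondary endpoints.** The synopsis lists PASI as one. Section 5.2 has none, and section 13.4 says "There are no secondary endpoints".

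**The concern.** PASI is a graded score. Reducing it to yes/no in 10 patients has two costs. First, if non-responders are a minority, the smaller group may hold two patients, one or none. With none there is no contrast. With one, a rank test cannot reach 5% whatever the data. Second, even a balanced split throws away the differences in improvement within each group. The synopsis cites the cost of molecular profiling as a reason for the small sample, so avoidable loss of information matters here. No analysis text links expression to PASI on its own scale, so nothing in the plan recovers what a split would lose.

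**Working it through.** **1. The plan's own figure.** Section 13.6 says 10 samples will detect two-fold differences. Power, dispersion and group split are not given, so the figure cannot be reproduced. As a range, take a per-sample log-scale SD of √(1/50 + CV²), with an assumed mean count of 50 and biological CV of 0.3 to 1.0. Two-sided power at 5% is approximately Φ(ln 2 / [SD·√(1/a + 1/b)] − 1.96) for group sizes a and b. Example: CV 0.3 gives SD = √0.11 = 0.332. At 5:5 the ratio is 0.693/(0.332 × 0.632) = 3.30, so power is Φ(1.34) = 91%.

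| Split | Power, CV 0.3 | Power, CV 1.0 |
|---|---|---|
| 5:5 | 91% | 19% |
| 7:3 | 86% | 17% |
| 8:2 | 75% | 14% |
| 9:1 | 51% | 10% |

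Whether 10 samples suffice therefore depends on a split that the plan neither states nor controls.

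**2. Number of non-responders.** With assumed response rate r and independent patients, P(0) = r¹⁰ and P(1) = 10(1 − r)r⁹. At r = 0.8, 0.107 + 0.268 = 0.376.

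**3. Information kept by a split.** For a normally distributed response linearly related to expression, the efficiency of a cut relative to the continuous score is φ(z_r)²/[r(1 − r)], a large-sample result. At r = 0.5, 0.399²/0.25 = 0.637. At r = 0.9, 0.1755²/0.09 = 0.342.

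| Assumed response rate | P(0 non-responders) | P(0 or 1) | Information lost |
|---|---|---|---|
| 50% | 0.1% | 1.1% | 36% |
| 60% | 0.6% | 4.6% | 38% |
| 70% | 2.8% | 14.9% | 42% |
| 80% | 10.7% | 37.6% | 51% |
| 90% | 34.9% | 73.6% | 66% |

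Under this model 10 patients carry the information of about 6.4 at 50% response and 3.4 at 90%.

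**4. Smallest attainable p.** For a two-sided exact rank test with k non-responders it is 2/C(10, k). This is 2/10 = 0.20 for k = 1 and 2/45 = 0.044 for k = 2.

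**5. Power at n = 10.** Simulated bivariate normal data, one gene, unadjusted two-sided 5%. A Pearson test on the continuous score is compared with a pooled t-test on the split. A 9:1 split is tested (8 degrees of freedom), and an empty group counts as no rejection.

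| Assumed correlation | Continuous | Split, 50% response | Split, 70% | Split, 80% |
|---|---|---|---|---|
| 0.8 | 87% | 59% | 51% | 40% |

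At a correlation of 0.5 the figures are about 33% continuous against roughly 15% to 21% split over the same response rates. With Bonferroni over an assumed 15,000 genes, at a correlation of 0.8, power is about 0.7% continuous and below 0.1% split.

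**The case against.** The strongest reply is that the documents do not commit to the split. Section 3.1 is an objective, not an analysis. The synopsis wording on correlating with response, and section 2, leave a continuous analysis open. No PASI cut-off exists, so no dichotomising rule has been written, and section 13 promises a detailed SAP. This stands, and it rules out saying that the plan has fixed on an analysis that discards a known share of the data. It does not remove the point: 3.1 is worded as binary, the only specified test is a two-group one, and nothing provides for PASI as a covariate.

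A reader might also infer that the trial may have no computable primary test. That goes too far. The synopsis comparison of diseased with normal skin does not depend on the number of non-responders, though it would not answer 3.1. Only the responder contrast fails, and only when a group is empty. A parametric test with one non-responder can still be run, weakly.

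Two further replies hold in part. This is a self-described pilot, so some of the choice is preference. And the power figures come from Gaussian data for a single gene; the power of the recommended Negative Binomial model was not simulated.

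**Conclusion.** The point holds in conditional form. Section 3.1 poses a binary question in 10 patients, with no response rate, cut-off or minimum number of non-responders, and the other sections do not settle the contrast.

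If response is dichotomised, the chance of 0 or 1 non-responder runs from about 1% to 74% across assumed response rates of 50% to 90%. The documents support the upper part of that range only loosely, by calling non-responders to biologics a minority. The 36% to 66% loss rests on a normal response, a linear relation and the same range of rates. It is not a figure from the protocol, and 66% is not a ceiling: the same formula gives about 78% at 95% response.

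The single-gene gain from a continuous analysis is real under the model. It should not be read as showing that 10 patients suffice for a gene screen: after multiplicity control both approaches have very little power.

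The conflict over PASI as a secondary endpoint is a separate consistency error and lends no weight to the argument about dichotomising.

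**What to change.** 1. **Section 13.3.** Make the main analysis a per-gene Negative Binomial regression of per-patient pre-treatment lesional counts (per cell population where single-cell data are used) on percent PASI improvement from baseline to the visit 16 weeks after first dose, as a continuous covariate. Keep responder versus non-responder as supportive, with its cut-off stated in advance. Align the synopsis with this.
2. **Section 9 and Appendix 1.** Add PASI scoring at Visit 1 or 2, before the first dose, and at Visit 4. Visit 4 falls 4 + 12 = 16 weeks after Visit 2, when treatment starts.
3. **Section 13.6.** State the assumed response rate and the resulting chance of fewer than two non-responders.
4. **Separately,** reconcile the synopsis with sections 5.2 and 13.4 on whether PASI is a secondary endpoint.

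**Cost.** This is more than SAP wording. PASI has to be put into the visit schedule, a small edit for an assessment the protocol already intends, but one that needs IRB approval as an amendment under section 15.1. The model family stays the same. The model assumes linearity, and a slope is less familiar than a group contrast. Improvement cannot exceed 100%, so values may bunch there and leave one or two non-responders with high leverage; a rank-based sensitivity analysis would check this. The change does not supply multiplicity control.

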3.2 Secondary Objectives

There is no secondary objective.

4 STUDY DESIGN

4.1 Study Overview

This is a single center study in which patients with psoriasis or atypical psoriasis will donate small samples of that skin and/or normal tissue prior to treatment with the FDA-approved psoriasis medication, tildrakizumab.

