2 STUDY RATIONALE

The researchers want to find a way to predict whether a person with psoriasis will respond to a given medication. In this study, patient will start tildrakizumab (a FDA-approved medication for psoriasis). Prior to treatment, a small piece of psoriasis-affected skin will be sampled and molecularly profiled. We will then analyze the molecular profiles and compare to patient tildrakizumab treatment response to predict which future patients will best respond to this medication.

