9 EVALUATIONS BY VISIT

9.1 Visit 1

1. Review the study with the subject (subject's legal representative) and obtain written informed consent and HIPAA authorization and assent, if appropriate.
2. Assign the subject a unique screening number.
3. Record demographics data.
4. Record medical history, including a history of rash, diagnosis date, and prior treatments.

5. Record concomitant medications.
6. Perform a complete skin examination.
7. Clean skin, anesthetize skin, take skin sample(s) (up to 2 6 mm punch biopsies), place suture.
8. Photograph of biopsied lesional skin and other psoriatic lesions
9. Part of the biopsied specimen will be sent for standard histopathology (if no previous histopathology from a similar representative lesion has been done)
10. Schedule subject for suture removal in 14 days.
11. Baseline routine bloodwork (CBC, quant gold, HIV, HB surface Ag, Anti-HB surface AB, anti-HB core AB, hepatitis C antibody, BUN/Creatinine, AST/ALT)

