13.1 Data Sets Analyzed

All eligible patients who consent to the study and have a skin sample taken will have data analyzed.

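### The synopsis plans a diseased-versus-normal comparison, but no section requires normal skin, and 10 samples from 10 subjects leave none once each subject gives one psoriatic sample.

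*Combined protocol and SAP*

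**What the plan says.** Two comparisons are planned, and they need different tissue.

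- **Section 3.1** seeks genes whose expression in psoriatic skin differs between responders and non-responders.
- **The synopsis, Primary Analysis Plan**, compares diseased with normal skin in a two-group Negative Binomial comparison at 5% for a single test.

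The sections on collection and counting are as follows.

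- **Section 4.1:** patients "will donate small samples of that skin and/or normal tissue prior to treatment with the FDA-approved psoriasis medication, tildrakizumab".
- **Section 9.1, item 7:** "take skin sample(s) (up to 2 6 mm punch biopsies), place suture". No tissue type is given.
- **Section 13.1:** "All eligible patients who consent to the study and have a skin sample taken will have data analyzed".
- **Section 13.6:** "10 samples will be collected for initial analysis". It adds that two-fold differences will be detected at that size, without naming a comparison.
- **Synopsis:** 10 subjects.
- **Appendix 1:** a biopsy at Visit 1 only, with no tissue type.

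Other places point to psoriatic skin. The synopsis primary objective is "To obtain pre-treatment psoriatic skin samples for molecular profiling prior to treatment with tildrakizumab to correlate with and to predict treatment response". Section 2 states: "Prior to treatment, a small piece of psoriasis-affected skin will be sampled and molecularly profiled". Section 9.1, item 8 calls for "Photograph of biopsied lesional skin and other psoriatic lesions".

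**The concern.** The diseased-versus-normal comparison depends on a group of samples that nothing in the protocol secures. Normal skin is mentioned as something that may be donated, but no section says from whom, how many, or whether it comes from the same patient as the lesional sample. If the second punch is discretionary, any normal samples will come from an unplanned subset of patients. In an unpaired comparison, tissue type is then partly mixed with who the patient is.

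The timing makes this more than a drafting matter. The only biopsy is at Visit 1 and the first dose is given at Visit 2. Section 13 promises a detailed SAP before the final analysis, but that document can only choose among samples already in hand.

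The wording of Sections 4.1 and 13.1 is also looser than Section 3.1 needs. Read alone, they would accept a subject with normal skin only, who could contribute nothing to a comparison within psoriatic skin.

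**Working it through.** **1. Counting samples.** Inputs: 10 subjects (synopsis), at most 2 punches per subject (Section 9.1, item 7), 10 samples (Section 13.6). Let L be lesional samples, N normal samples and T = L + N.

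| Reading | L | N | T | Agrees with 10 samples? | Normal group? |
|---|---|---|---|---|---|
| One psoriatic sample from each of 10 subjects | 10 | 0 | 10 | yes | none |
| The same, plus normal skin from k subjects (k = 1 to 10) | 10 | k | 10 + k, so 11 to 20 | no | k samples |
| T held at 10 with N at least 1, 10 subjects | at most 9 | at least 1 | 10 | yes | yes, but at least one subject has no lesional sample |

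A total of 10 therefore cannot supply a lesional sample from each of 10 subjects and any normal sample as well. This uses only the documents' own figures.

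**2. Tissue type, section by section.** Sections 4.1 and 13.1 accept either tissue. Section 9.1, item 7 is silent. The synopsis objective and Sections 2 and 3.1 require psoriatic skin, and Section 9.1, item 8 presupposes it. None of these requires normal skin. The synopsis analysis plan uses normal skin but does not say where it comes from.

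**3. The two-fold statement in Section 13.6.** It can be neither reproduced nor refuted, because power, dispersion and group split are not given. An illustration shows why it must name its comparison. On the log scale:

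power ≈ Φ( δ / [σ √(1/n₁ + 1/n₂)] − 1.96 ), with δ = ln 2 = 0.693.

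The level is two-sided 5% (sidedness is not stated) and the groups are treated as independent. The SD σ is an assumption, set at 0.5 and varied from 0.3 to 1.0.

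Worked case, 10 lesional and 10 normal at σ = 0.5: 0.693 / (0.5 × √0.2) = 3.10; 3.10 − 1.96 = 1.14; Φ(1.14) = 0.87.

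| Comparison | Samples | Power, σ = 0.5 | Power, σ = 0.3 to 1.0 |
|---|---|---|---|
| Diseased vs normal | 10 and 0 | cannot be run | cannot be run |
| Diseased vs normal | 10 and 10 (20 in all) | 0.87 | 0.999 to 0.341 |
| Responder vs non-responder, lesional | 5 and 5 | 0.59 | 0.955 to 0.194 |
| Responder vs non-responder, lesional | 7 and 3 | 0.52 | 0.917 to 0.170 |
| Responder vs non-responder, lesional | 8 and 2 | 0.42 | 0.832 to 0.139 |
| Responder vs non-responder, lesional | 9 and 1 | 0.26 | 0.592 to 0.096 |

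For 80% power, σ could be at most 0.55 with 10 and 10, but at most 0.39 with 5 and 5. The normal approximation is optimistic at these sizes. No multiplicity adjustment is made, in line with the synopsis wording, and within-patient pairing would alter the first comparison. The table serves only to show that the same headline of 10 describes very different situations.

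**The case against.** The best reply is that the protocol plainly intends psoriatic skin from every patient. The synopsis objective and Section 2 say so. Visit 1, item 8 has the biopsied lesion photographed, and item 9 sends part of the specimen for histopathology where no similar lesion has been examined before. Section 9.2 mentions histopathology consistent with psoriasis (if none was done previously) among the matters considered before dosing. With 10 subjects stated, 10 samples naturally means one each. This reply stands, and it disposes of three stronger readings.

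- *A reader might infer that normal-only donors are a real prospect.* Section 4.1 alone permits them, but the sections just listed make them improbable. It is a conflict of wording.
- *A reader might infer that two punches per subject would end the study at 5 subjects, with a responder comparison of, say, 3 versus 2.* The synopsis fixes 10 subjects, Section 12.4 replaces withdrawals, and nothing stops enrolment at the tenth punch.
- *A reader might infer that neither comparison is assured.* On the natural reading the responder comparison has its lesional tissue. What threatens it is the absence of a PASI response cut-off and the uncontrolled number of non-responders, which are separate matters.

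It is also fair to say that the synopsis plans a two-group comparison and promises no pairing, so the absence of paired tissue does not in itself break the plan. None of this supplies a normal sample, however. The sections that secure lesional tissue are silent on normal tissue, and the natural reading of the count is the one that leaves none.

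**Conclusion.** The point holds for the diseased-versus-normal comparison. Its second group is not required by any section and is zero on the most natural reading of 10 subjects and 10 samples. That result is arithmetic on the plan's own figures. For the responder comparison, the finding is limited to an inconsistency: Sections 4.1 and 13.1 are looser than Sections 2 and 3.1, the synopsis objective and Visit 1, item 8. The two-fold statement in Section 13.6 cannot be assigned to either comparison as written. The power figures rest on assumed SDs and are illustrative; the conclusion does not depend on them. The correction is worth making before further biopsies are taken, because missing pre-treatment tissue cannot be recovered.

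**What to change.** All changes stay within the existing limit of two punches.

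- **Sections 4.1 and 9.1, item 7:** state that every subject gives one lesional sample, and that a second punch, when taken, is normal skin from the same subject.
- **Section 13.1:** require a lesional sample for inclusion in the Section 3.1 analysis.
- **Section 13.6:** give the size as *10 lesional samples, one from each of 10 subjects, plus any paired normal samples*. Name the comparison to which the two-fold statement applies, with the power, dispersion and group split assumed.
- **Synopsis, Primary Analysis Plan:** make diseased-versus-normal an exploratory comparison in subjects with both tissues, with subject as a blocking factor. The alternative is for the sponsor to take the second punch in everyone. One of the two is needed, because the first three edits alone leave normal skin optional.

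The cost is wording in four places, loss of the option to use the second punch on a second lesion, and the profiling of any normal samples: up to 10 more if every subject is paired. The synopsis already cites profiling cost as a reason for the small number of patients. Where no earlier histopathology exists, the single lesional punch must serve both histopathology and profiling; item 9 already foresees dividing the specimen.
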